## 9. MEASUREMENT OF EFFECT

### Antitumor Effect – Solid Tumors

For the purposes of this study, patients should be re-evaluated for response every nine weeks.

If treatment is held for adverse event recovery thereby extending cycle length, then imaging and tumor measurement intervals may be correspondingly altered so that the patient is imaged every third cycle.

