### **5. DOSING DELAYS/DOSE MODIFICATIONS**

#### **5.1 5-FU/Capecitabine**

A dose reduction will be instituted upon any grade 3 or 4 toxicity that is attributable to 5-FU/capecitabine. For all grade 3 or 4 toxicities related to 5-FU/capecitabine, the study treatment will be withheld for up to 3 weeks until the toxicity has resolved to CTCAE grade 1 or better (or back to baseline), and then treatment may be restarted. Dose reduction/re-challenge for each toxicity criterion will be managed as discussed in the sections that follow. Patients will be withdrawn from the study if toxicity does not resolve to  $\leq$  CTCAE grade 1 (or to baseline) within 3 weeks.

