## **5.2 Interferon Alpha-2b**

A dose reduction will be instituted upon any grade 3 or 4 toxicity that is attributable to Interferon alpha-2b. For all grade 3 or 4 toxicities related to IFN, the study treatment will be withheld for up to 3 weeks until the toxicity has resolved to CTCAE grade 1 or better, and then treatment may be restarted. Dose reduction/re-challenge for each toxicity criterion will be managed as discussed in the sections that follow. Patients will be withdrawn from the study if toxicity does not resolve to  $\leq$  CTCAE grade 1 within 3 weeks.

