#### **9.5 Progression-Free Survival**

Progression-free survival (PFS) is defined as the duration of time from start of treatment to time of progression or death, whichever occurs first.

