## **11. STATISTICAL CONSIDERATIONS**

### **11.1 Study Endpoints**

#### 11.1.1 Primary Objective

To establish the objective response rate to IFN alpha-2b and 5-FU/capecitabine using RECIST criteria in patients with unresectable/metastatic CSCC after 3 cycles of treatment (9 weeks).

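### On-treatment scans may be moved with toxicity holds, so recorded progression times depend partly on tolerability and site choice, and 3 cycles no longer equals 9 weeks

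*Combined protocol and SAP*

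**What the plan says.** All references are to the combined protocol and SAP.

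- **Section 9, opening text.** The base rule is "For the purposes of this study, patients should be re-evaluated for response every nine weeks". The exception follows at once. It applies when a hold for toxicity lengthens a cycle, and in that case the plan says that "imaging and tumor measurement intervals may be correspondingly altered so that the patient is imaged every third cycle". The verb is permissive, so the site may move the scan or leave it.
- **Section 5.1 (5-FU/capecitabine).** For related grade 3 or 4 toxicity, "the study treatment will be withheld for up to 3 weeks until the toxicity has resolved to CTCAE grade 1 or better". Section 5.2 has a matching rule for interferon: "For all grade 3 or 4 toxicities related to IFN, the study treatment will be withheld for up to 3 weeks". I found no stated limit on the number of holds.
- **Section 5.1, specific toxicities.** Under the myelosuppression, mucositis/hand-foot and other-toxicity rules, treatment is discontinued once a hold reaches 3 weeks. The diarrhoea rule withdraws the patient only when a hold exceeds 3 weeks.
- **Section 9.5.** PFS is the "duration of time from start of treatment to time of progression or death", whichever comes first. Section 11.4 plans Kaplan-Meier medians and 6- and 12-month rates.
- **Section 11.1.1.** Response is assessed "in patients with unresectable/metastatic CSCC after 3 cycles of treatment (9 weeks" in parentheses. Section 11.2 repeats the 3 cycles and gives no weeks.
- **Section 8.** In the copy I worked from, the calendar marks tumour measurement and radiologic evaluation at pre-study only. It gives no on-treatment scan weeks.

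I found no scan window, no calendar-based scan during a hold, and no analysis rule for late scans.

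**The concern.** Radiologic progression is dated when it is seen, so the scan schedule is part of the PFS measurement. A schedule that stretches with toxicity ties a patient's recorded progression time to how well treatment was tolerated. Because the shift is optional, two patients with identical holds can also be scanned in different weeks.

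The 6-month rate is the most exposed figure. It depends on which scan was the last before the landmark, and a hold changes that scan.

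Sections 11.1.1 and 11.2 also need a single anchor. After a hold that lengthens a cycle, the end of cycle 3 and week 9 are different dates, and the plan does not say which one governs.

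The point concerns scan timing on treatment, not imaging after treatment ends.

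**Working it through.** **1. Timing of the first scan.** The inputs are 21-day cycles (Section 4), 3 cycles (Section 11.1.1) and holds of up to 3 weeks (Section 5).

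- No hold: 3 × 3 = 9 weeks, which is the plan's own figure.
- One hold of 1, 2 or 3 weeks: 9 + 1, 9 + 2 or 9 + 3 = week 10, 11 or 12.
- Two full 3-week holds: 9 + 6 = week 15. This is an extreme. It needs two complete holds, each under a rule that does not discontinue at 3 weeks.

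**2. Individual patients do not all move the same way.** Compare scans at weeks 9, 18, 27 with scans at weeks 12, 21, 30 after one 3-week hold.

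- True progression at week 8: recorded at week 12 instead of week 9, which is later.
- True progression at week 10: recorded at week 12 instead of week 18, which is earlier.

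**3. Average effect for a held patient.** The documents give neither a PFS assumption nor a hold rate. I assume exponential PFS with true median m of 12 to 39 weeks and λ = ln 2 / m. I also assume that progression is seen only at scans, that scans continue every 9 weeks after the first, and that the hold itself does not change the true progression time.

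- Mean recorded PFS with first scan at week f: f + 9·exp(−fλ) / (1 − exp(−9λ)).
- Recorded 26-week rate: exp(−λs), where s is the last scan at or before week 26. On the common schedule s = 18. After one 3-week hold s = 21.

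| Assumed median (weeks) | Mean recorded PFS, f = 9 | f = 12 | Change | 26-week rate, s = 18 | s = 21 | Change |
|---|---|---|---|---|---|---|
| 12 | 22.2 | 23.1 | +0.9 | 0.354 | 0.297 | −0.057 |
| 18 | 30.7 | 31.4 | +0.6 | 0.500 | 0.445 | −0.055 |
| 26 | 42.2 | 42.6 | +0.5 | 0.619 | 0.571 | −0.048 |
| 39 | 60.9 | 61.2 | +0.3 | 0.726 | 0.689 | −0.037 |

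Changes in the mean are taken before rounding. With two full holds (f = 15) the mean rises by 0.8 to 2.1 weeks.

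The recorded median moves either way. With one hold against none it is 21 against 18 weeks (true 18) and 30 against 27 (true 26), but 12 against 18 (true 12) and 39 against 45 (true 39).

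**4. Whole-trial effect.** If a share h of patients has one such hold, the 26-week rate changes by h times the last column. With h = 0.40 (assumed):

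- median 18: 0.6 × 0.500 + 0.4 × 0.445 = 0.478, against 0.500;
- median 26: 0.6 × 0.619 + 0.4 × 0.571 = 0.600, against 0.619.

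Both are falls of about 2 points. With h = 0.20 or 0.60 the fall is about 1 or 3 points.

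**5. Response design.** Under the Section 11.2 rule (continue with at least 2 of 16 responses, succeed with at least 5 of 25), exact two-stage binomial calculation gives alpha 0.0951 at a 10% response rate and power 0.903 at 30%. Both meet the stated 0.1 and 0.1. Scan timing does not enter this calculation.

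**The case against.** The strongest defence is that the primary endpoint is cycle-based. Section 11.2 says 3 cycles with no weeks, and the weeks in Section 11.1.1 can be read as the arithmetic of three 21-day cycles. Imaging after the third cycle keeps exposure equal across patients at the response reading. This stands. Reading a patient with a 3-week hold at week 9 would mean judging response after only about 2 cycles. Best overall response (Section 9.3.3) also runs until progression, so a shifted scan need not lose a response.

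The size is also limited, for reasons that largely stand:

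- Three of the Section 5.1 toxicity rules discontinue treatment when a hold reaches 3 weeks, so resuming after a full 3-week hold is not available under them.
- Several Section 5.2 rules hold interferon alone and need not lengthen the cycle, which is the trigger in Section 9.
- Detection is not purely by scan. There is a physical examination each cycle, and superficial lesions may be measured clinically (Section 9.2). Resumption after other toxicities requires no evidence of progression (Section 5.1).
- The trial has one arm and PFS is secondary and descriptive. At a rate of 0.5, an approximate 95% half-width is 1.96 × √(0.25/n), or 18 to 20 points for n = 30 to 25. A 2-point shift is small beside that.
- At one patient every 1 to 2 months (Section 11.3), 16 patients take about 16 to 32 months to accrue, so stage-1 data arriving a few weeks late matters little.

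None of this supplies a scan window or a late-scan rule, and none says whether 3 cycles or 9 weeks governs after a hold.

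**Conclusion.** The point holds as one of toxicity-dependent ascertainment. Section 9 lets on-treatment scan dates move with holds at the site's discretion, while PFS is counted in calendar time and summarised at fixed landmarks. It also leaves the two descriptions of the response time point in Section 11.1.1 unreconciled after a hold.

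The size is modest. The first scan moves to weeks 10 to 12 after one hold. For a patient held 3 weeks, mean recorded PFS rises by under 1 week and the recorded 26-week rate falls by about 4 to 6 points. The overall fall is about 2 points if 40% are held. These figures rest on an assumed exponential model, assumed medians of 12 to 39 weeks and an assumed hold rate.

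A reader might infer three stronger conclusions, which are not supported:

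- *Postponed scans systematically lengthen PFS.* The mean rises slightly, the 26-week rate falls, and the median goes either way.
- *The response-rate decision is compromised.* The 2-of-16 and 5-of-25 rule and its error rates are unchanged, and the endpoint is itself defined by cycles.
- *Treatment comparisons are biased.* There is no second arm. What suffers is the interpretation of the PFS estimates.

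**What to change.** Replace the Section 9 exception with wording such as: *Tumour assessments are done every 9 weeks (± 7 days), counted from the first day of treatment, until progression. They are not moved for dose holds or cycle delays.*

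Enter this in the Section 8 calendar as a repeating schedule. It should not stop at weeks 9, 18 and 27. Nine undelayed cycles already take 9 × 3 = 27 weeks, so patients with holds are treated beyond that, and scans should continue past week 27 while treatment continues.

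Do not redefine the primary endpoint as the week-9 scan. Reconcile Sections 11.1.1 and 11.2 instead, for example by reading the 3-cycle response at the first scheduled scan on or after completion of cycle 3. All earlier scheduled scans would still count for response and progression.

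The change leaves dose and hold rules, sample size and decision rules as they are, and the number of scans is about the same. It has two costs. Some scans will fall mid-cycle. The 3-cycle reading of a held patient may also come some weeks later than now: with one 3-week hold, cycle 3 ends at week 12 and the next scheduled scan is week 18, so 18 − 12 = 6 weeks later, give or take the window.

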#### 9.1 Definitions

Response and progression will be evaluated in this study using the new international criteria proposed by the Response Evaluation Criteria in Solid Tumors (RECIST) v1.1 Committee [JNCI 92(3):205-216, 2000]. Changes in only the largest diameter (unidimensional measurement) of the tumor lesions are used in the RECIST criteria. Note: Lesions are either measurable or non-measurable using the criteria provided below. The term “evaluable” in reference to measurability will not be used because it does not provide additional meaning or accuracy.

##### 9.1.1 Measurable disease

Measurable lesions are defined as those that can be accurately measured in at least one dimension (longest diameter to be recorded) as  $\geq 10$  mm with conventional techniques (CT, MRI, x-ray). All tumor measurements must be recorded in millimeters (or decimal fractions of centimeters).

### 9.1.2 Non-measurable disease

All other lesions (or sites of disease), including small lesions (longest diameter <20 mm with conventional techniques or <10 mm using spiral CT scan), are considered non-measurable disease. Bone lesions, leptomeningeal disease, ascites, pleural/pericardial effusions, lymphangitis, inflammatory breast disease, abdominal masses (not followed by CT or MRI), and cystic lesions are all non-measurable.

### 9.1.3 Target lesions

All measurable lesions up to a maximum of five lesions per organ and 10 lesions in total, representative of all involved organs, should be identified as **target lesions** and recorded and measured at baseline. Target lesions should be selected on the basis of their size (lesions with the longest diameter) and their suitability for accurate repeated measurements (either by imaging techniques or clinically). A sum of the longest diameter (LD) for all target lesions will be calculated and reported as the baseline sum LD. The baseline sum LD will be used as reference by which to characterize the objective tumor response.

### 9.1.4 Non-target lesions

All other lesions (or sites of disease) should be identified as **non-target lesions** and should also be recorded at baseline. Non-target lesions include measurable lesions that exceed the maximum numbers per organ or total of all involved organs as well as non-measurable lesions. Measurements of these lesions are not required, but the presence or absence of each should be noted throughout follow-up.

## 9.2 Guidelines for Evaluation of Measurable Disease

All measurements should be taken and recorded in metric notation using a ruler or calipers. All baseline evaluations should be performed as closely as possible to the beginning of treatment and never more than 4 weeks before the beginning of the treatment.

The same method of assessment and the same technique should be used to characterize each identified and reported lesion at baseline and during follow-up. Imaging-based evaluation is preferred to evaluation by clinical examination when both methods have been used to assess the antitumor effect of a treatment.

**Clinical lesions.** Clinical lesions will only be considered measurable when they are superficial (e.g., skin nodules and palpable lymph nodes). In the case of skin lesions, documentation by calipers or color photography (including a ruler to estimate the size of the lesion) is recommended.

**Conventional CT and MRI.** These techniques should be performed with cuts of 10 mm or less in slice thickness contiguously. Spiral CT should be performed using a 5 mm contiguous reconstruction algorithm. This applies to tumors of the chest, abdomen, and pelvis. Head and neck tumors and those of extremities usually require

specific protocols.

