### **3. PATIENT SELECTION**

#### **3.1 Inclusion Criteria**

- 3.1.1 Patients must have histologically or cytologically confirmed squamous cell carcinoma of the skin. Patients who present with "squamous cell carcinoma of unknown primary lesions" at the time of diagnosis will be eligible if patients have a plausible primary skin site removed in the past. Similarly, patients with neck, parotid, or facial lymph nodes positive for squamous cell carcinoma with no identifiable mucosal primary would also be eligible.

- 3.1.2 Patients must have measurable disease, defined by RECIST v1.1 as at least one lesion that can be accurately measured in at least one dimension of  $\geq 10$  mm by CT, MRI, or calipers. See section 9.2 for the evaluation of measurable disease.
- 3.1.3 There is no limitation to prior treatments with local, regional, topical or systemic agents, except for prior systemic treatment with 5-fluorouracil or prodrugs thereof. Prior topical treatment with 5-fluorouracil is permitted. Patients who are on chronic daily doses of prednisone of greater than 10 mg are excluded. There is no restriction on timing of last treatments as long as patients have recovered from all expected toxicities and at least 21 days have passed since last administration.
- 3.1.4 Age  $\geq 18$  years. Because no dosing or adverse event data are currently available on the use of 5-FU/Capecitabine or IFN alpha-2b in patients  $<18$  years of age, children are excluded from this study.
- 3.1.5 Life expectancy of greater than 3 months.
- 3.1.6 ECOG performance status  $\leq 2$  (Karnofsky  $\geq 60\%$ ; see Appendix A).
- 3.1.7 Patients must have normal organ and marrow function as defined below:
 

Absolute neutrophil count	$\geq 1,500/\text{mcL}$
Platelets	$\geq 75,000/\text{mcL}$
Total Bilirubin	$< \text{ULN}$ or up to 2x ULN if patient has clinically documented Gilbert's syndrome (elevated unconjugated bilirubin from decreased UGT1A1 activity)
AST(SGOT)/ALT(SGPT)	$\leq 2.5x$ institutional upper limit of normal or up to 5x ULN if known to be caused by liver metastasis
Creatinine Clearance	$\geq 50 \text{ mL/min}$ by either Cockcroft-Gault formula or 24 hr urine collection analysis.

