### 9.3 Response Criteria

#### 9.3.1 Evaluation of target lesions

Complete Response (CR): Disappearance of all target lesions

Partial Response (PR): At least a 30% decrease in the sum of the longest diameter (LD) of target lesions, taking as reference the baseline sum LD

Progressive Disease (PD): At least a 20% increase in the sum of the LD of target lesions, taking as reference the smallest sum LD recorded since the treatment started or the appearance of one or more new lesions

Stable Disease (SD): Neither sufficient shrinkage to qualify for PR nor sufficient increase to qualify for PD, taking as reference the smallest sum LD since the treatment started

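### Section 9.2 permits 10 mm CT/MRI cuts while 3.1.2 and 9.1.1 accept 10 mm lesions as measurable, which adds slice-position error to the response endpoint for small targets and conflicts with 9.1.2

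*Combined protocol and SAP*

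**What the plan says.** Four parts of the combined protocol and SAP bear on this point.

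- **Acquisition (9.2).** For conventional CT and MRI: "These techniques should be performed with cuts of 10 mm or less in slice thickness contiguously". For spiral CT: "Spiral CT should be performed using a 5 mm contiguous reconstruction algorithm". The scope is then limited: "This applies to tumors of the chest, abdomen, and pelvis". Head-and-neck and extremity tumors are referred to specific protocols, with no slice limit given. The same method and technique must be used at baseline and follow-up.
- **Smallest measurable lesion.** Eligibility criterion 3.1.2 requires one lesion of at least 10 mm "by CT, MRI, or calipers". Section 9.1.1 also sets 10 mm and names CT, MRI and x-ray as conventional techniques. Section 9.1.2 instead makes a lesion non-measurable below 20 mm by conventional techniques, or below 10 mm by spiral CT.
- **Response (9.3.1, 9.4.1).** Partial response is "At least a 30% decrease in the sum of the longest diameter (LD) of target lesions", relative to baseline, and must be confirmed by a repeat assessment 4 weeks later.
- **Decision rule (11.2).** At least 2 responders in the first 16 patients, then at least 5 in 25, for response rates of 10% against 30% with both error rates at 0.1.

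**The concern.** On 3.1.2 and 9.1.1, one lesion about as large as a single permitted slice is enough for entry and can be the whole target sum. On slices that thick, the in-plane diameter depends on where the slice boundaries fall, and that position is not reproduced between scans even when the technique is the same. A smaller lesion also loses proportionally more of its apparent diameter than a larger one, so true shrinkage can look greater than it is.

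The primary endpoint is a threshold on that diameter, and the go/no-go decision turns on a handful of responders, so a few misclassified patients could matter. The plan holds spiral CT to 5 mm but gives no reason to let other CT or MRI of the same lesions run to 10 mm.

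**Working it through.** **The plan's own figure.** Exact binomial enumeration of the rule (at least 2/16, then at least 5/25) gives a type I error of 0.095 at 10% and power of 0.903 at 30%. The stated design is reproduced.

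**Model.** The documents give no figure for measurement error, so this is illustrative. Assumptions: one spherical target of diameter D = 2R; contiguous slices of thickness T at a random position on each scan; edge drawn where the lesion fills at least a fraction f of the slice, with f = 0.25 or 0.5; baseline reading at least 10 mm.

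Let a be the distance from the lesion centre to the nearest slice boundary, uniform on 0 to T/2. The largest in-slice reading is

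d = 2√(R² − h²), with h = max(fT/2, fT − a).

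So h lies between fT/2 and fT. A follow-up reading is at most 70% of baseline when

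h_F² ≥ R_F² − 0.49(R_B² − h_B²).

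A confirmed response needs this on two independent follow-up scans against the same baseline.

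**Worked case: 15 mm shrinking 20% (to 12 mm).** R_B² = 56.25 and R_F² = 36, so the condition is h_F² ≥ 8.44 + 0.49h_B².
- T = 10, f = 0.5: h runs from 2.5 to 5, and half of all positions sit at 2.5. With h_B = 2.5 the condition is h_F ≥ √11.5 = 3.39, with probability 0.5 × (5 − 3.39)/2.5 = 0.32. Averaged over baseline positions this is 27% on one scan and about 8% confirmed.
- T = 5, f = 0.5, or T = 10, f = 0.25: h never exceeds 2.5, but at least √(8.44 + 0.49 × 1.25²) = 3.03 is needed, so 0%.

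**All cases** (single scan / confirmed):

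| True change | 10 mm, f = 0.25 | 10 mm, f = 0.5 | 5 mm, f = 0.25 | 5 mm, f = 0.5 |
|---|---|---|---|---|
| 15 mm, −20% | 0 / 0 | 27% / 8% | 0 / 0 | 0 / 0 |
| 15 mm, −25% | 5% / 0.3% | 40% / 17% | 0 / 0 | 8% / 0.9% |
| 20 mm, −25% | 0 / 0 | 30% / 10% | 0 / 0 | 0 / 0 |

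**Error in the other direction.** A 15 mm lesion that truly falls 32% has R_F² = 5.1² = 26.01. The call is missed when h_F² < 0.49h_B² − 1.55. On 10 mm slices at f = 0.5 this happens in about 12% of single scan pairs; on 5 mm slices, never. At f = 0.25 it is 0% for both.

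**Unchanged lesions on 10 mm slices.** The condition becomes h_F² ≥ 0.51R² + 0.49h_B². At 15 mm, 0.51 × 56.25 = 28.7 already exceeds the largest possible h² of 25, so the rate is 0%, and likewise for larger lesions. An unchanged 12 mm sphere at f = 0.5 gives about 7% on one scan and under 1% confirmed. A true 10 mm sphere at f = 0.5 reads at most 2√(25 − 6.25) = 8.7 mm, so it would not reach the floor at baseline.

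**Scale for the decision rule.** If a share q of true non-responders were falsely called responders, the apparent rate under the null is 0.10 + 0.90q. For q = 1% (0.109) the type I error is 0.126; for q = 2% (0.118) it is 0.160. These values of q are assumed. Neither the model nor the documents supply them.

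**The case against.** The case for leaving 9.2 alone is substantial. The 10 mm figure is a ceiling, spiral CT is set at 5 mm, and superficial lesions may be measured clinically. Section 9.1.3 selects the largest lesions suited to repeated measurement. Section 9.1.2 already pairs 20 mm with conventional techniques and 10 mm with spiral CT. Confirmation cuts the single-scan rates of 27%, 40% and 30% to about 8%, 17% and 10%. Drawing the edge at 25% fill instead of 50% takes the same single-scan rates to 0%, 5% and 0%.

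Most of this stands, and it limits the size of the point. It does not remove it. Section 9.1.2 is contradicted by 3.1.2 and 9.1.1, so it cannot be relied on as written. Confirmation reuses the same baseline, so an error there carries through. Extra targets do not reliably help either: at 50% fill, several 15 mm lesions all shrinking 25% are misread more often than one, because the under-reading is systematic.

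A reader might infer two stronger things. The first is that partial-volume error alone turns stable disease into response. The model does not show this: unchanged lesions of 15 mm or more give 0%, and the notable rates need a true fall of 20% to 25%. The second is that 10 mm cuts cannot measure a 30% change. That is too absolute: at 50% fill, a true 30% fall at 15 mm is called a response in about 83% of scan pairs on both 10 mm and 5 mm slices.

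**Conclusion.** The point holds in a limited form. As written, the plan allows a target no larger than one slice and contradicts itself on whether that lesion is measurable. For small targets on thick cuts, this adds error in both directions to the primary endpoint, mainly for lesions whose true change is already near 30%.

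For a single 15 mm target, the modelled confirmed false-response rate on 10 mm against 5 mm slices is 0.3% to 17% against 0% to 1% for a true 25% fall, and 0% to 8% against 0% for a true 20% fall. These ranges rest on a spherical lesion, random slice position and an edge rule of 25% to 50% fill, none of which the documents give.

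The share of patients with only small targets on thick conventional cuts is unknown. The documents therefore do not support a claim that the trial's type I error is inflated by any stated amount. Severity is minor to moderate.

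**What to change.** In 9.2, require contiguous slices of 5 mm or less for every CT and MRI used to measure target lesions, at baseline and follow-up. This extends the protocol's own spiral-CT setting and also covers body regions that now have no limit.

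Reconcile 3.1.2 and 9.1.1 with 9.1.2, so that for imaging the 10 mm floor applies only to scans meeting that requirement. The caliper criterion in 3.1.2 is not affected. Where only thicker slices exist, apply the 20 mm floor already in 9.1.2 and treat smaller lesions as non-target. This fallback is the weaker safeguard: a 20 mm lesion shrinking 25% still gives 0% to 10% confirmed on 10 mm slices. The 5 mm rule should therefore come first.

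The cost is one sentence in 9.2 and a wording alignment in the measurability sections. A few small lesions on thick-slice scans become non-target, or an MRI series needs thinner slices. A patient whose only lesion is 10 to 19 mm on such a scan would need a thinner-slice scan to qualify on imaging.
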